#### 4.3 Final Analyses

## Statistical Analysis Plan (SAP)

---

Final analyses will be conducted following final database lock (DBL). Unblinded TFLs and a CSR with completed time points will be provided.

## Statistical Analysis Plan (SAP)

### 5 Study Endpoints

Table 2 summarizes the study endpoints in relation to their corresponding study objectives, as well as a brief overview of the statistical methods (described in greater detail in Section 8) used to analyze each endpoint.

**Table 2: Study Objective, Endpoint, and Statistical Methodology Overview**

Primary Objectives	Primary Endpoints	Statistical Methodology
Primary Objective #1: To evaluate the safety and tolerability of repeat intramuscular (IM) administration of G03-52-01 in healthy adult subjects	Primary Endpoint #1a: The occurrence of adverse events (AEs) and serious adverse events (SAEs) following administration of G03-52-01 to the final visit	Incidence rate of the various AE categories, and the counts and percentages of subjects that experienced them
	Primary Endpoint #1b: The occurrence of changes from baseline in PE, vital signs, and clinical safety laboratory values following administration of G03-52-01 to the final follow-up visit	Descriptive statistics for the change/shift from baseline in laboratory (chemistry and hematology), vital signs (heart rate, blood pressure, respiratory rate, pulse oximetry, and body temperature), and physical examination measures
Primary Objective #2: For Cohorts 1-3 (Cohorts 1-2 active IP and Cohort 3 is placebo): 
 
Demonstrate target protective concentration (NAC) value > 0.02 U/mL (BoNT/A) or > 0.03 U/mL (BoNT/B) at Day 45 and Day 90
 
To evaluate lot-to-lot variability of two doses of G03-52-01
 
	Primary Endpoint #2: For Cohorts 1-3, to evaluate the proportion of subjects with target protective concentration (NAC) value > 0.02 U/mL (BoNT/A) or > 0.03 U/mL (BoNT/B) at Day 45 and Day 90 (Note: There will be no formal statistical analysis to support evaluation of lot-to-lot variability. In table summaries, the two lots within each of Cohorts 1 and 2 will be summarized and displayed separately to visually assess lot-to-lot variability.)	Protective NAC rate at Day 45 and Day 90, where protective NAC rate is defined as the proportion of subjects with NAC value > 0.02 U/mL against BoNT/A or NAC value > 0.03 U/mL against BoNT/B
Primary Objective #3: For Cohort 4 (active IP only), demonstrate target protective concentration (NAC) value of BoNT/A and BoNT/B at 4 and 8 hours post-dose	Primary Endpoint #3: For Cohort 4, to evaluate the proportion of subjects with target protective concentration (NAC) value > 0.02 U/mL (botulinum neurotoxin [BoNT]/A) or > 0.03 U/mL (BoNT/B) at 4 and 8 hours post dose	Protective NAC rate at 4 Hours and 8 Hours post dose, where protective NAC rate is defined as the proportion of subjects with NAC value > 0.02 U/mL against BoNT/A or NAC value > 0.03 U/mL against BoNT/B
Secondary Objectives	Secondary Endpoints	Statistical Methodology
Secondary Objective #1: For Cohorts 1-3 (Cohorts 1-2 active IP and Cohort 3 is placebo): Demonstrate target protective concentration (NAC) value > 0.02 U/mL (BoNT/A) or > 0.03 U/mL (BoNT/B) at Day 120	Secondary Endpoint #1: To evaluate target protective concentration (NAC) value > 0.02 U/mL (BoNT/A) or > 0.03 U/mL (BoNT/B) at Day 120	Protective NAC rate at Day 120, where protective NAC rate is defined as the proportion of subjects with NAC value > 0.02 U/mL against BoNT/A or NAC value > 0.03 U/mL against BoNT/B
Secondary Objective #2: For Cohorts 1-3 (Cohorts 1-2 active IP and Cohort 3 is placebo): To evaluate pharmacodynamic (PD) and anti-drug antibody (ADA) at pre-dose through the end of study	Secondary Endpoint #2: Descriptive statistics of selected PD and ADA at all timepoints tested	Summary statistics [number of subjects (n), mean, standard deviation (SD), median, first quartile, third quartile, minimum, maximum], coefficient of variation (CV, presented in percentage, CV%), geometric mean (GM), the 95%

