1. PROTOCOL SYNOPSIS

Name of Sponsor/Company: Resilience Government Services, Inc.	Individual Study Table Referring to Part of the Dossier: Volume: Page:	(For National Authority Use Only)
Name of Investigational Product: G03-52-01		
Name of Active Ingredient: NX01, NX02, NX11, XB10, XB18, and XB23		
Protocol Number: G03-52-01-002		
Title of Study: A Phase 2, Randomized, Double-Blinded, Placebo-Controlled Study to Evaluate the Safety, Tolerability, Pharmacodynamics, and Immunogenicity of G03-52-01 in Adult Subjects		
Study Center(s): Approximately 15 sites		
Phase of Development: Phase 2		
Study Duration: Approximately 8 months		
Subject Participation: Subject’s participation in Cohort 1-3 of the study is approximately 254 days (up to a 14-day screening, 1-hour inpatient stay and 240 days outpatient follow-up) Subject’s participation in Cohort 4 is approximately 134 days (up to a 14-day screening, 8-hour inpatient stay and 120 days outpatient follow-up)		
Objectives and Endpoints:		
Primary Objectives	Primary Endpoints	

 • To evaluate the safety and tolerability of single or repeat intramuscular (IM) administration of G03-52-01 in healthy adult subjects • Cohorts 1-3 
 ○ Demonstrate target protective concentration (NAC) value of BoNT/A and BoNT/B through Day 45 and Day 90 ○ To evaluate lot-to-lot variability of the two doses of G03-52-01 • For Cohort 4, demonstrate target protective concentration (NAC) value of BoNT/A and BoNT/B at 4 and 8 hours post dose 	
 • The occurrence of adverse events (AEs) and serious adverse events (SAEs) following administration of G03-52-01 to the final visit • The occurrence of changes from baseline in physical examination (PE), vital signs, and clinical safety laboratory values following administration of G03-52-01 to the final follow-up visit • For Cohorts 1-3, to evaluate target protective concentration (NAC) value > 0.02 U/mL (botulinum neurotoxin [BoNT]/A) or > 0.03 U/mL (BoNT/B) at Day 45 and Day 90 • For Cohort 4, to evaluate the proportion of subjects with target protective concentration (NAC) value > 0.02 U/mL (botulinum neurotoxin [BoNT]/A) or > 0.03 U/mL (BoNT/B) at 4 and 8 hours post dose 	

Secondary Objectives:
	
Secondary Endpoints:

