4. OBJECTIVES

4.1. Study Objectives

Primary Objective:

- To evaluate the safety and tolerability of single or repeat IM administration of G03-52-01 in health adult subjects
- For Cohorts 1-3
 - Demonstrate target protective concentration (NAC) value > 0.02 U/mL (BoNT/A) or > 0.03 U/mL (BoNT/B) at Day 45 and Day 90
 - To evaluate lot-to-lot variability of two doses of G03-52-01
- For Cohort 4, demonstrate target protective concentration (NAC) value of BoNT/A and BoNT/B at 4 and 8 hours post dose

Secondary Objective:

- Cohorts 1-3
 - Demonstrate target protective concentration (NAC) value > 0.02 U/mL (BoNT/A) or > 0.03 U/mL (BoNT/B) at Day 120
 - To evaluate pharmacodynamic (PD) and anti-drug antibody (ADA) at pre-dose through the end of study
- Cohort 4
 - Demonstrate target protective concentration (NAC) value of BoNT/A and BoNT/B at 2 hours post dose
 - To assess pharmacokinetics (PK) at pre-dose through end of study
 - To evaluate pharmacodynamic (PD) and anti-drug antibody (ADA) at pre-dose through the end of study

Exploratory Objectives:

- For Cohorts 1-3, to evaluate PK parameters to ensure ADA evaluation adequate of the two lots

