### 2 Study Objectives

#### 2.1 Primary Objectives

- To evaluate the safety and tolerability of single or repeat intramuscular (IM) administration of G03-52-01 in healthy adult subjects
- For Cohorts 1-3 (Cohorts 1-2 active IP and Cohort 3 is placebo)
  - Demonstrate target protective concentration (NAC) value  $> 0.02$  U/mL (BoNT/A) or  $> 0.03$  U/mL (BoNT/B) at Day 45 and Day 90
  - To evaluate lot-to-lot variability of two doses of G03-52-01 (Note: There will be no formal statistical analysis to support evaluation of lot-to-lot variability. In table summaries, the two lots within each of Cohorts 1 and 2 will be summarized and displayed separately to visually assess lot-to-lot variability.)
- For Cohort 4 (only active IP), demonstrate target protective concentration (NAC) value of BoNT/A and BoNT/B at 4 and 8 hours post-dose

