## Statistical Analysis Plan (SAP)

		confidence interval (CI) for GM, the geometric coefficient of variation (GCV, presented in percentage, GCV%), and the 95% CI of GCV% calculated for each time point for each cohort and DP lot
Secondary Objective #3: For Cohort 4 (only active IP): Demonstrate target protective concentration (NAC) value of BoNT/A and BoNT/B at 2 hours post-dose	Secondary Endpoint #3: To evaluate the proportion of subjects with target protective concentration (NAC) value > 0.02 U/mL (botulinum neurotoxin [BoNT]/A) or > 0.03 U/mL (BoNT/B) at 2 hours post dose	Protective NAC rate at 2 Hours post dose, where protective NAC rate is defined as the proportion of subjects with NAC value > 0.02 U/mL against BoNT/A or NAC value > 0.03 U/mL against BoNT/B
Secondary Objective #4: For Cohort 4 (only active IP): To assess pharmacokinetics (PK) at pre-dose through end of study	Secondary Endpoint #4: PK analysis at the determined timepoints	Summary statistics [number of subjects (n), mean, SD, median, first quartile, third quartile, minimum, maximum], CV%, GM, the 95% CI for GM, GCV%, and the 95% CI of GCV% calculated for each time point for the Cohort 4 active G03-52-01 treatment group
Secondary Objective #5: For Cohort 4 (only active IP): To evaluate pharmacodynamics (PD) and anti-drug antibody (ADA) at pre-dose through the end of study	Secondary Endpoint #5: Descriptive statistics of determined PD and ADA timepoints	Summary statistics [number of subjects (n), mean, SD, median, first quartile, third quartile, minimum, maximum], CV%, GM, the 95% CI for GM, GCV%, and the 95% CI of GCV% calculated for each time point for the Cohort 4 active G03-52-01 treatment group
Exploratory Objective	Exploratory Endpoint	Statistical Methodology
Exploratory Objective: For Cohorts 1-3 (Cohorts 1-2 active IP and Cohort 3 is placebo): To evaluate PK parameters to ensure ADA evaluation adequate of the two lots	Exploratory Endpoint: Descriptive statistics of selected PK parameters at all time points tested of the two lots	Summary statistics [number of subjects (n), mean, SD, median, first quartile, third quartile, minimum, maximum], CV%, GM, the 95% CI for GM, GCV%, and the 95% CI of GCV% calculated for each time point for each cohort and DP lot

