### 9.10.3 Primary Endpoint 2 – Target Protective NAC (Day 45 and Day 90), Cohorts 1-2

To evaluate primary objective #2, to demonstrate target protective concentration (NAC) value of BoNT/A and BoNT/B through Day 45 and Day 90 for Cohorts 1-2, primary endpoint #2 will be used:

For Cohorts 1-2, to evaluate target protective concentration (NAC) value  $> 0.02$  U/mL (BoNT/A) or  $> 0.03$  U/mL (BoNT/B) at Day 45 and Day 90

PD samples will be collected and analyzed by the Battelle MNA against serotypes BoNT/A and BoNT/B at Baseline/Dosing [Visit 2 (Day 1)] pre-dose, Visit 3 (24 Hours), Visit 5 (Day 8), Visit 6 (Day 15), Visit 7 (Day 45) pre-dose, Visit 8 (Day 49), Visit 10 (Day 90), and Visit 11 (Day 120).

At Visit 7 (Day 45) and Visit 10 (Day 90), the frequency and percentage of subjects with a NAC  $> 0.02$  U/mL against BoNT/A, a NAC  $> 0.03$  against BoNT/B, and those with either a NAC  $> 0.02$  U/mL against BoNT/A or a NAC  $> 0.03$  U/mL against BoNT/B will be presented. Percentages will be based on the total number of subjects at the respective time point with evaluable concentrations. Summaries will be presented for each lot separately within each of the two active drug cohorts.

The PD population will be used for the analysis of this primary endpoint.

### 9.10.4 Primary Endpoint 3 – Target Protective NAC (4 Hours and 8 Hours), Cohort 4

To evaluate primary objective #3, to demonstrate target protective concentration (NAC) value of BoNT/A and BoNT/B at 4 and 8 Hours post-dose for Cohort 4 (active only), primary endpoint #3 will be used.

At 4 Hours post-dose and 8 Hours post-dose, the frequency and percentage of subjects with a NAC  $> 0.02$  U/mL against BoNT/A, a NAC  $> 0.03$  against BoNT/B, and those with either a NAC  $> 0.02$  U/mL against BoNT/A or a NAC  $> 0.03$  U/mL against BoNT/B will be presented. Percentages will be based on the total number of subjects at the respective time point with evaluable concentrations. Summaries will be presented for each lot separately within each of the two active drug cohorts.

The PD population will be used for the analysis of this primary endpoint.

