## Statistical Analysis Plan (SAP)

---

To evaluate target protective concentration (NAC) value  $> 0.02$  U/mL (BoNT/A) or  $> 0.03$  U/mL (BoNT/B) at Day 120

At Visit 11 (Day 120), the frequency and percentage of subjects with a NAC  $> 0.02$  U/mL against BoNT/A, a NAC  $> 0.03$  against BoNT/B, and those with either a NAC  $> 0.02$  U/mL against BoNT/A or a NAC  $> 0.03$  U/mL against BoNT/B will be presented. Percentages will be based on the total number of subjects at the respective time point with evaluable concentrations. Summaries will be presented for each lot separately within each of the two active drug cohorts.

The PD population will be used for the analysis of this secondary endpoint.

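### SAP Table 2 calls being above either toxin's target the protective NAC rate, no planned row gives the share above both targets, and the 2-hour rate is planned at 4 and 8 hours

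*SAP*

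**What the plan says.** SAP section 5, Table 2, attaches the term protective NAC rate to Primary Endpoints 2 and 3 and Secondary Endpoints 1 and 3. Each time the rate is "defined as the proportion of subjects with NAC value > 0.02 U/mL against BoNT/A or NAC value > 0.03 U/mL against BoNT/B".

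SAP 9.10.3, 9.10.4, 9.10.5 and 9.10.7 turn this into three rows: above the A target, above the B target, "and those with either a NAC" above its target for A or for B. The third row shows that the 'or' is inclusive. Percentages use subjects with evaluable concentrations at the time point. No section lists a row for subjects above both targets.

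The objectives are worded differently from the rate:

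- Cohort 4, SAP 2.1: "For Cohort 4 (only active IP), demonstrate target protective concentration (NAC) value of BoNT/A and BoNT/B at 4 and 8 hours post-dose". Table 2 repeats this for Primary Objective 3.
- Cohort 4, SAP 2.2 and Table 2, Secondary Objective 3: "Demonstrate target protective concentration (NAC) value of BoNT/A and BoNT/B at 2 hours post-dose".
- Cohorts 1-2, opening of SAP 9.10.3: "to demonstrate target protective concentration (NAC) value of BoNT/A and BoNT/B through Day 45 and Day 90 for Cohorts 1-2". SAP 2.1 and Table 2 state the same objective with the two thresholds joined by 'or'.
- The supplied protocol shows the same split for Cohorts 1-3. The synopsis has "Demonstrate target protective concentration (NAC) value of BoNT/A and BoNT/B through Day 45 and Day 90", while section 4.1 has "Demonstrate target protective concentration (NAC) value > 0.02 U/mL (BoNT/A) or > 0.03 U/mL (BoNT/B) at Day 45 and Day 90".

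SAP 9.10.7 covers Secondary Endpoint 3. Its heading and endpoint sentence say 2 hours. Its restated objective and its planned rows say 4 and 8 hours.

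**The concern.** G03-52-01 combines three antibodies against BoNT/A and three against BoNT/B (Protocol 3.1.3), so being above target for one toxin does not establish the same for the other. Under the Table 2 label, a subject above target for A and below it for B is counted in a rate called protective. A reader of that rate alone could take it to mean coverage of both toxins, which is one natural reading of the objectives worded with 'and'.

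The figure that would settle the matter, the share above both targets, is not a planned output. At stake is how a primary descriptive result is named and read. No test, error rate or sample size depends on it.

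The time-point error in 9.10.7 is a separate drafting fault in the same set of endpoints. Followed literally, it leaves a specified secondary rate untabulated.

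**Working it through.** The plan gives no rate, power or sample-size figure for these endpoints, so there is no figure to reproduce. The check uses set identities and a comparison of sections.

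**Inputs.** The three planned rows come from SAP 9.10.3-9.10.5 and 9.10.7. The illustration uses n = 30, the number of Cohort 4 active subjects whose PD samples are tested (SAP 3.4). The counts above each target are assumptions, because the documents give none.

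**Identities.** Let A and B be the numbers above each target.

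- both = A + B − either
- either lies between max(A, B) and min(n, A + B)
- both lies between max(0, A + B − n) and min(A, B)
- either − both = number of discordant subjects, which is at least |A − B|

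So the either rate can never fall below the better serotype, and the both rate can never exceed the worse one.

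**Illustrations with n = 30.**

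| Assumed A, B | Either | Both | Gap |
|---|---|---|---|
| 27, 27 | 27 to 30 (90-100%) | 27 down to 27 + 27 − 30 = 24 (90-80%) | 0 to 6 subjects (0-20 points) |
| 27, 21 | 27 to 30 (90-100%) | 21 down to 27 + 21 − 30 = 18 (70-60%) | 6 to 12 subjects (20-40 points) |
| 30, 21 | 30 (100%) | 21 (70%) | 9 subjects (30 points) |

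The first row shows that equal rates can give no gap at all. The last shows a rate labelled protective at 100% while 30% of subjects are below the B target.

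**Can the both rate be recovered from the planned output?** The count can, from the first identity. The percentage needs n_AB, the number evaluable for both serotypes. With n_A and n_B evaluable for each serotype and n_any evaluable for at least one, n_AB = n_A + n_B − n_any. This works only if all three denominators are shown. SAP 9.10.3 refers just to evaluable concentrations at the time point, without saying whether one or both serotypes are meant. SAP 7.1.4 admits a subject to the PD population on one serotype. If only one common denominator is printed, n_AB cannot be worked out from the table, although the subject-level NAC listings (SAP 9.10.6, 9.10.9) would allow it.

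**Consistency of the objective wording.** Within the SAP alone, 9.10.3 uses 'and' for Cohorts 1-2, whereas 2.1 and Table 2 use 'or'. For Cohort 4, 2.1, 2.2 and Table 2 all use 'and', beside a rate defined with 'or'.

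**The 2-hour rate.** Table 2 specifies it for Secondary Endpoint 3. In section 9 only 9.10.7 covers that endpoint, and its rows are at 4 and 8 hours, the same times as 9.10.4. The Cohort 4 NAC summary in 9.10.9 lists pre-dose, 24 hours and Days 30, 45 and 90, and gives NAC values rather than threshold rates. No part of section 9 as written tabulates a 2-hour rate.

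**The case against.** The best defence is that the plan already shows what matters. Table 2 is introduced as an overview. The term protective NAC rate does not recur in section 9, where the A and B rows come first and the either row is not ranked above them. Table shells are in a separate document (SAP section 1), so the printed label is unknown. The protocol endpoints in 4.2 are themselves worded with 'or', and Protocol 3.1.3 describes the use under study as botulism from A and/or B. The 'and' in the objectives may simply name the two serotypes measured. Subject-level values are listed, the count above both follows by subtraction, and nothing is formally tested.

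Most of this stands, and it rules out several stronger readings that a reader might infer:

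- *That the union is the headline result and hides a weak serotype.* Separate rows are planned and section 9 gives the union no priority.
- *That the documents require coverage of both toxins, so the SAP departs from the protocol.* No objective states a joint rule for each subject, and the SAP follows the 'or' of the protocol endpoint.
- *That the rate will be inflated by a known amount.* The gaps above rest wholly on assumed counts.
- *That later values below the quantitation limit, which SAP 8.3 sets to missing, should be counted as below target in these rows.* That is valid only if the assay limit does not exceed the target, and the documents do not state the limit.

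The protocol comparison also has a limit. The SAP is written to protocol version 5.0 of 06-JAN-2025, while the protocol supplied is dated 12 Apr 2024 and its change log ends at Version 4.0. The comparison within the SAP does not depend on this.

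The defence leaves three things unanswered: Table 2 does attach the word protective to the union four times, no row shows the share above both targets, and the denominator is not defined by serotype. Nor does it excuse the time points in 9.10.7.

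**Conclusion.** The point holds as a matter of labelling and one missing row. Under the Table 2 definition, a subject below target for one toxin counts towards the protective NAC rate, and the proportion above both targets is not planned. The overstatement relative to that proportion equals the discordant share, at least |A − B|. It is near zero if both serotype rates are high and concordant, and tens of percentage points if one serotype lags. The documents do not show which case applies.

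The 2-hour error is a plain internal inconsistency. It should not be read as the loss of the endpoint: Table 2 and the heading and endpoint sentence of 9.10.7 still specify 2 hours, and samples are planned at that time.

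Both should be corrected before the tables are produced. No data are lost, and no alpha or power figure changes, since SAP section 6 plans no formal testing. The conclusion rests on the SAP text as supplied, with the table shells and protocol version 5.0 not seen.

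**What to change.** 1. In SAP Table 2, for all four endpoints, label the union 'above at least one target' instead of protective NAC rate.
2. In 9.10.3, 9.10.4, 9.10.5 and 9.10.7, keep the A, B and either rows. Add the proportion above both targets among subjects evaluable for both serotypes at that time point, with that denominator shown.
3. Use one wording of the NAC objective for Cohorts 1-3 throughout the SAP.
4. Correct the restated objective and the planned rows in 9.10.7 to 2 hours.
5. Check the wording against protocol version 5.0, and record any departure in SAP section 10, which now lists none.

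The cost is one extra row in each affected table and some text edits. No new samples, assays or data are needed. The added row can never exceed the either row, so the change cannot be seen as favouring the product.

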## Statistical Analysis Plan (SAP)

		confidence interval (CI) for GM, the geometric coefficient of variation (GCV, presented in percentage, GCV%), and the 95% CI of GCV% calculated for each time point for each cohort and DP lot
Secondary Objective #3: For Cohort 4 (only active IP): Demonstrate target protective concentration (NAC) value of BoNT/A and BoNT/B at 2 hours post-dose	Secondary Endpoint #3: To evaluate the proportion of subjects with target protective concentration (NAC) value > 0.02 U/mL (botulinum neurotoxin [BoNT]/A) or > 0.03 U/mL (BoNT/B) at 2 hours post dose	Protective NAC rate at 2 Hours post dose, where protective NAC rate is defined as the proportion of subjects with NAC value > 0.02 U/mL against BoNT/A or NAC value > 0.03 U/mL against BoNT/B
Secondary Objective #4: For Cohort 4 (only active IP): To assess pharmacokinetics (PK) at pre-dose through end of study	Secondary Endpoint #4: PK analysis at the determined timepoints	Summary statistics [number of subjects (n), mean, SD, median, first quartile, third quartile, minimum, maximum], CV%, GM, the 95% CI for GM, GCV%, and the 95% CI of GCV% calculated for each time point for the Cohort 4 active G03-52-01 treatment group
Secondary Objective #5: For Cohort 4 (only active IP): To evaluate pharmacodynamics (PD) and anti-drug antibody (ADA) at pre-dose through the end of study	Secondary Endpoint #5: Descriptive statistics of determined PD and ADA timepoints	Summary statistics [number of subjects (n), mean, SD, median, first quartile, third quartile, minimum, maximum], CV%, GM, the 95% CI for GM, GCV%, and the 95% CI of GCV% calculated for each time point for the Cohort 4 active G03-52-01 treatment group
Exploratory Objective	Exploratory Endpoint	Statistical Methodology
Exploratory Objective: For Cohorts 1-3 (Cohorts 1-2 active IP and Cohort 3 is placebo): To evaluate PK parameters to ensure ADA evaluation adequate of the two lots	Exploratory Endpoint: Descriptive statistics of selected PK parameters at all time points tested of the two lots	Summary statistics [number of subjects (n), mean, SD, median, first quartile, third quartile, minimum, maximum], CV%, GM, the 95% CI for GM, GCV%, and the 95% CI of GCV% calculated for each time point for each cohort and DP lot

